11.4 Early Termination

With effective oral therapy, immediate relief of all symptoms is not expected and subjects should not expect immediate relief.

If the subject experiences persistence or worsening or recurrence of symptoms that per the investigator's assessment (e.g., symptoms ≥ 3) warrant the use of rescue antifungal therapy, a vaginal examination with investigator's rating of signs should be completed. Additionally, vulvovaginal samples should be obtained for KOH testing and pH measurements by the local laboratory, fungal culture by the central laboratory and investigation of other pathogens such as bacterial vaginosis and *Trichomonas vaginalis* by the local laboratory.

If the KOH test is negative, the investigator should consider other causes for the persistence or worsening of the symptoms as antifungal rescue medication may not be indicated.

If the investigator's rating of the vulvovaginal signs and vaginal sample collection is not possible prior to the initiation of the rescue therapy, it should still be completed as soon as possible after rescue therapy is initiated.

In addition to the vaginal examination, the symptoms that led to the use of rescue antifungal therapy should be documented in the eCRF and the following procedures should also be completed:

- If rescue therapy is administered prior to or at the TOC visit, all TOC visit procedures should be completed and no additional visits will be needed. The subject will be considered as early termination due to lack of efficacy prior to or at TOC.
- If rescue therapy is administered after the TOC visit but prior to or at the FU visit, all FU visit procedures should be completed and no additional visits will be needed. The subject will be considered as early termination due to lack of efficacy after TOC but prior to or at FU.

Oral fluconazole [one 150-mg dose] may be provided to study sites as rescue medication. However, at the investigator's discretion other approved antifungal agent may be administered as rescue medication to a particular patient for whom fluconazole is not considered the optimal option. All rescue antifungal medications should be documented in the eCRF.

Details of study treatment groups and dietary requirements for treatment administration are provided in [Section 12.1](#) and [Section 12.2](#), respectively.

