18.2 Analysis Populations

The study populations to be used in the analyses are defined as follows:

Intent-to-Treat (ITT) Population: All randomized subjects.

Modified Intent-to-Treat (mITT) Population: All randomized subjects who have a positive culture for *Candida* species at Baseline.

Per-Protocol (PP) Population: All mITT subjects who have completed the study drug treatment AND who have a TOC evaluation.

Safety Population: All randomized subjects who received at least one dose of study drug and who have at least one post-Baseline evaluation.

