21.0 Appendices

Appendix A: Prohibited Medications and Medications to be Administered with Caution

Prohibited Medications

The use of any topical vaginal corticoids and topical vaginal contraceptives is prohibited during the study. No systemic or topical vaginal antifungal treatment other than the study drug is allowed during the study unless used as rescue medication after the subject has been documented as not responding to study drug. No investigational drugs other than the study drug are allowed within 30 days before Screening and for the entire duration of the study. In addition, the medications listed below are also prohibited.

Strong CYP3A4/5 inhibitors and CYP3A4/5 inducers

CYP	Strong Inhibitors ^a	Inducers ^a	
3A4/5	
 • boceprevir • clarithromycin • conivaptan • indinavir • lopinavir • mibefradil 	
 • nefazodone • nelfinavir • ritonavir • saquinavir • telaprevir • telithromycin 	
 • avasimibe • carbamazepine • phenytoin • rifampin • St. John's wort • long-lasting barbiturates

- a. The CYP3A4/5 inhibitors and CYP3A4/5 inducers listed in this table are not permitted during the 7 days prior to enrollment and during study treatment until TOC.

P-glycoprotein (P-gp) substrates

P-gp Drug Substrates ^a
digoxin, colchicine

- a. The P-gp substrates listed in this table are not permitted during the 48 hours prior to enrollment or during study treatment

Medications to be administered with Caution and Monitored as Appropriate

CYP3A4 substrates

CYP	Substrates
3A4	
In vitro, ibrexafungerp (SCY-078) was an inhibitor of CYP3A mediated metabolism of midazolam, but was only a weak inhibitor of metabolism of testosterone. The clinical significance of this inhibition is unknown; caution should be exercised when administering ibrexafungerp (SCY-078) with drugs known to be CYP3A sensitive substrates with narrow therapeutic index, such as midazolam and cyclosporine.
 
Subjects receiving sirolimus, tacrolimus, warfarin, cyclosporine or amiodarone are permitted for enrollment in the study and these medications may be administered concomitantly with ibrexafungerp (SCY-078) with close monitoring. Dosing adjustments and subsequent monitoring of sirolimus and warfarin should be undertaken in accordance with product prescribing information for the respective agents.

OATP1B3 substrates

OATP	Substrate

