Unless otherwise specified, baseline will be defined as the last non-missing assessment prior to or on the date (and time if appropriate) of the first dose of study drug. Change from baseline is defined as: post-baseline value – baseline value.

The study day will be calculated as follows:

If the assessment date occurs on or after the date of the first dose of study drug:

$$\text{Study day} = \text{assessment date} - \text{first dose date} + 1.$$

If the date of interest occurs before the date of the first dose of study drug:

$$\text{Study day} = \text{assessment date} - \text{first dose date}$$

There is no study day 0.

All analyses will be conducted using SAS Version 9.3 or higher. All statistical tests will be two-sided and interpreted at a 5% significance level.

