4.1. Sample Size

The primary endpoint of the study is the percentage of subjects achieving a clinical cure at the TOC visit. Assuming clinical cure rates of 50% and 30% for ibrexafungerp and placebo administered in a 2:1 ratio, respectively, approximately 282 subjects will provide 90% power to detect a difference between ibrexafungerp and placebo based on a Pearson’s Chi-squared test with a Type 1 error rate of 5%. Because it is expected that approximately 20% of subjects may not have a mycological culture-confirmed infection at Baseline and approximately 10% may withdraw early

from the study, an additional 84 subjects are added for a total of 366 subjects (244 subjects randomized to ibrexafungerp and 122 subjects, to placebo).

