4.3. Analysis Set

Intent-to-Treat (ITT) Set: All randomized subjects who signed the consent form and received at least one dose of study drug.

Modified Intent-to-Treat (mITT) Set: All randomized subjects who have a positive culture for Candida species at baseline and taking at least one dose of study drug.

Per-Protocol (PP) Set: All mITT subjects who meet all of the following criteria:

- Completed the study drug treatment;
- Have a TOC evaluation that includes documentation of signs, symptoms and collection of a vaginal culture;
- No major protocol deviation.

Safety Set (SS): All randomized subjects who received at least one dose of study drug and who have at least one post-baseline evaluation.

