8.1. Primary Endpoint

The primary efficacy endpoint is defined as the proportion of mITT subjects who have a clinical cure (complete resolution of signs and symptoms) at the test-of-cure (TOC) visit.

Clinical outcomes will be assessed at the TOC Visit (Day 11) according to the following definitions:

- Clinical cure: Complete resolution of signs and symptoms of vulvovaginal infection without need for further antifungal treatment and topical vaginal drug therapy for the treatment of vulvovaginal irritation/pruritus prior to or at the TOC visit. Specifically, for complete resolution, any sign or symptom should be absent (score = 0);
- Clinical failure: No response to therapy or incomplete resolution of signs and symptoms or use of additional vulvovaginal or systemic antifungal therapy or topical vaginal drug therapy for the treatment of vulvovaginal irritation/pruritus prior to or at the TOC visit. For the subject who early terminated before TOC visit and received additional vulvovaginal or systemic antifungal therapy or topical vaginal drug therapy for the treatment of vulvovaginal irritation/pruritus prior to or at the early termination visit, the subject is considered a clinical failure.

Signs of VVC will be defined as the presence of erythema, edema, or excoriation. Symptoms of VVC will be defined as itching, burning, or irritation.

Each vulvovaginal sign will be objectively scored based on severity as follows:

- 0 = none (complete absence of any signs or symptoms);
- 1 = mild (slight);
- 2 = moderate (definitely present);
- 3 = severe (marked, intense).

Each vulvovaginal symptom will be objectively scored based on severity as follows:

- 0 = none (I have no discomfort);
- 1 = mild (I have some discomfort, but it does not bother me much);
- 2 = moderate (I have discomfort, which is annoying, but not enough to affect what I am doing);
- 3 = severe (I have discomfort, which is annoying enough to affect what I am doing).

The composite score of the vulvovaginal signs and symptoms will be calculated according to the following rules and this scale has a total possible score of 18.

- If all items of the vulvovaginal signs and symptoms have been scored, the composite score is calculated as the sum of the individual scores of all 3 items of signs and 3 items of symptoms;
- If any sign or symptom is not done, the composite score will not be calculated and treated as a missing data except at FU visit;

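### The SAP's per-protocol set can drop women already classed as failures for using antifungal or topical therapy, and SAP section 11 does not list the narrower definition as a change

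*SAP*

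**What the plan says.** Protocol 18.2 defines the PP population as "All mITT subjects who have completed the study drug treatment AND who have a TOC evaluation". SAP 4.3 keeps the completed-drug condition and makes the second one stricter: "Have a TOC evaluation that includes documentation of signs, symptoms and collection of a vaginal culture". It then adds a third, that there be no major protocol deviation. SAP section 11 lists two departures from the protocol (ANCOVA in place of ANOVA, and the diabetes factor in the models). The PP definition is not among them.

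SAP 8.1 counts as clinical failure "incomplete resolution of signs and symptoms or use of additional vulvovaginal or systemic antifungal therapy", and also topical vaginal therapy for irritation or itching, up to TOC. It applies this to women who terminate before TOC as well. SAP 8.2.1 has a parallel rule that makes antifungal use before TOC a mycological persistence.

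Protocol 11.4 foresees cases where "vaginal sample collection is not possible prior to the initiation of the rescue therapy". The same sentence asks for the rating and sample as soon as possible afterwards, and the section asks for all TOC procedures when rescue is given at or before TOC. Protocol 11.3 asks the same of women who discontinue before TOC. Appendix A bars other antifungals "unless used as rescue medication after the subject has been documented as not responding to study drug", and bars topical vaginal corticoids outright. SAP 5.2 leaves the choice of major deviations to a separate rules document and a review before database lock.

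SAP section 8 makes mITT primary, with ITT and PP supportive.

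**The concern.** A woman who took an antifungal or a topical vaginal product before TOC has a known outcome under SAP 8.1: she is a clinical failure whatever her scores. Entry to PP nevertheless depends on her having a complete TOC record and no major deviation, and the medication use that fixes her outcome can also cause her to miss either condition. Selection into PP then depends on the outcome, because it can take out failures of this kind but never cures.

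PP is one of two analyses meant to support the primary result. If it differs from mITT, readers will look for an explanation in compliance or data quality. Under this rule, the selection itself could produce the difference.

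**Working it through.** **1. Routes out of PP, from the text.** A known failure can be lost in three ways:
- Her TOC signs, symptoms or culture are incomplete. Protocol 10.1.2 collects the culture before rescue only when that is possible.
- Her early-termination visit is not accepted as the TOC evaluation. SAP 8.1 speaks of the two visits separately, and SAP 4.3 does not say whether one can stand in for the other.
- She self-treated with a prohibited product and this is ruled a major deviation.

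SAP 4.3 exempts her from none of these. SAP 8.1.1 applies non-responder imputation to PP, but a set that requires a documented TOC evaluation leaves almost nothing to impute, so imputation does not bring her back.

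**2. Reproduce the plan's sample size.** Inputs are "Assuming clinical cure rates of 50% and 30% for ibrexafungerp and placebo administered in a 2:1 ratio" (SAP 4.1), 90% power, Pearson chi-squared, and "All statistical tests will be two-sided and interpreted at a 5% significance level" (SAP section 4). With pooled variance and no continuity correction, the average rate is (2 × 0.50 + 0.30)/3 = 0.4333, and

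n(placebo) = [1.960 × √(0.4333 × 0.5667 × 1.5) + 1.2816 × √(0.30 × 0.70 + 0.50 × 0.50/2)]² / 0.20² = (1.1895 + 0.7418)² / 0.04 = 93.2, rounded up to 94.

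This gives 94 + 188 = 282, as stated, with power 90.2%.

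**3. Effect of removing failures.** Failures at the planning rates are 94 of 188 (50%) on ibrexafungerp and 65.8 of 94 (70%) on placebo. Remove a fraction f_i of the first and f_p of the second. Cures stay at 94 and 28.2, so:
- PP cure rates are 94/(188 − 94 f_i) and 28.2/(94 − 65.8 f_p);
- the PP odds ratio is 2.33 × (1 − f_p)/(1 − f_i).

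The documents give no value for either fraction, so those below are assumptions.

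| f_i / f_p | Removed (ibrexafungerp, placebo) | PP cure rates | Difference (points) | Odds ratio |
|---|---|---|---|---|
| 0 / 0 | 0, 0 | 50.0% vs 30.0% | 20.0 | 2.33 |
| 20% / 20% | 18.8, 13.2 | 55.6% vs 34.9% | 20.7 | 2.33 |
| 5% / 10% | 4.7, 6.6 | 51.3% vs 32.3% | 19.0 | 2.21 |
| 10% / 20% | 9.4, 13.2 | 52.6% vs 34.9% | 17.7 | 2.07 |
| 10% / 30% | 9.4, 19.7 | 52.6% vs 38.0% | 14.7 | 1.81 |
| 20% / 10% | 18.8, 6.6 | 55.6% vs 32.3% | 23.3 | 2.63 |

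At equal fractions of 20%, placebo loses the larger share of its arm (13.2/94 = 14% against 18.8/188 = 10%) but the smaller number of women. It loses the larger number only if f_p exceeds 94/65.8 = 1.43 times f_i.

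The odds ratio falls once f_p exceeds f_i. The difference in points needs slightly more. With f_i = 10%, the placebo rate must pass 52.63% − 20% = 32.63%, so f_p must exceed (94 − 28.2/0.3263)/65.8 = 11.5%.

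**4. Illustration in whole women.** Expected mITT is 244 × 0.80 = 195 and 122 × 0.80 = 98, using the plan's 20% culture-negative allowance. Cures at the planning rates are 98 and 29.
- Start: 98/195 = 50.3%, 29/98 = 29.6%; difference 20.7 points.
- Remove 8 and 15 known failures (about 4% and 15% of each arm): 98/187 = 52.4%, 29/83 = 34.9%; difference 17.5 points.
- Remove 4 and 8 (about 2% and 8%): 98/191 = 51.3%, 29/90 = 32.2%; difference 19.1 points.

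**The case against.** The strongest reply is that a woman managed as the protocol intends will have a full record. Protocol 11.3 and 11.4 ask for all TOC procedures at early discontinuation or rescue, and SAP 4.3 needs a culture to be collected, not one taken before rescue. Rescue after documented non-response is permitted, so it is not in itself a deviation. Topical analgesics, which Protocol 18.6.1 names as failure-defining, are not on the prohibited lists. The protocol's own PP set already required a TOC evaluation, so a woman with none was excluded under both documents. The SAP adds only the incomplete evaluations and the major deviations. All of this stands, and it limits how many women are affected. It does not supply the missing exemption or settle the status of an early-termination visit.

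A reader might go further and infer that more placebo women will be removed, so that PP is biased against the drug. The documents do not support that. They give no rate of rescue, self-treatment or incomplete TOC data by arm. At equal removal fractions the odds ratio does not move, and the reverse imbalance widens the contrast. Nor can a reader infer that self-treatment will be ruled a major deviation, because the rules document is not part of the plan as provided.

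The SAP also plans summaries of disposition, rescue timing and major deviations, which would help to explain a discrepancy. They do not amount to a table of PP exclusions by arm and reason.

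**Conclusion.** The point holds as a flaw in the definition of a supportive set. As written, SAP 4.3 allows selection on outcome: where known failures are removed, the cure rate in that arm's PP set rises. The treatment contrast may shrink, stay put or widen, depending on removal fractions that nobody can state from the documents. Under the assumed removals in the illustration, the difference falls from 20.7 to 19.1 or 17.5 points. These sizes rest on the planning cure rates and on removal counts chosen for illustration.

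The primary mITT analysis keeps these women as failures, and ITT does too, so the primary conclusion is not at risk. What is at risk is the reading of PP, because a departure from mITT could be an artefact of the set's definition. The unlisted change from the protocol is a separate documentation gap and needs no assumption. Because the repair is wording only, it should be made.

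**What to change.** Before unblinding, amend the SAP as follows.

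- **SAP 4.3, membership:** keep in PP every mITT woman who completed study drug and either has a TOC evaluation with signs, symptoms and culture, or had medication use after dosing and up to TOC that SAP 8.1 makes a failure. Analyse the second group as clinical failures and, for antifungal use as SAP 8.2.1 provides, also as mycological persistence.
- **Topical-only users with no culture:** leave them out of the PP mycological and overall-outcome analyses, or state that they are imputed. For the overall outcome, SAP 8.2.2 already makes a clinical failure an overall failure, so keeping them there would need no imputed culture.
- **Deviations:** state that failure-defining medication use is not by itself a major deviation for PP.
- **Visits:** state whether an early-termination visit counts as the TOC evaluation.
- **Reporting:** tabulate PP exclusions by arm and reason.
- **SAP section 11:** list the changed PP definition.

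No new data are needed. The cost is a slightly larger PP set that includes some women with incomplete TOC data.

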4.4. Handing of missing data

For categorical response endpoints including clinical outcome, mycological outcome, symptom outcome, and clinical improvement, subjects will be considered a non-responder for the non-responder imputation (NRI) analysis if they do not meet the clinical response criteria for categorical responses or are missing categorical response data at the specific visit. Randomized subjects without at least 1 post-baseline observation will also be defined as non-responder for the NRI analysis such that subjects who have a missing value at the TOC visit or FU visit will be assigned as treatment failures, i.e., non-responders or positive mycological outcome for the corresponding visit. Randomized subjects without study treatment will be excluded from all analysis.

5. Subject Disposition

5.1. Disposition

A disposition of subjects includes the number and percentage of subjects for the following categories: subjects in each analysis set (ITT, mITT, PP, SS), subjects who completed TOC visit, subjects who completed the study (without need for antifungal treatment), subjects who completed the study (with need for antifungal treatment at FU visit), subjects who discontinued from the study, and the reasons for study discontinuation will be presented by the ITT and mITT sets. All percentages will be based on the number of subjects in each corresponding set.

The reason for study discontinuation may include any of the following: lack of efficacy and/or use of antifungal therapy prior to TOC; use of antifungal therapy after TOC (but prior to FU visit); adverse event; lack of efficacy after TOC; lost to follow-up; physician decision; pregnancy; study terminated by sponsor; study subject withdrawal by parent or guardian; withdrawal by subject; other; death, and trial screen failure.

Subject disposition data will be presented in a listing.

5.2. Protocol Deviations

The investigator may not deviate from the protocol without a formal protocol amendment having been established and approved by an appropriate IRB, except when necessary to eliminate immediate hazards to the subject or when the change(s) involve(s) only logistical or administrative aspects of the study.

Significant protocol deviations will be defined in the significant protocol deviations rules document. Each significant deviation will be assigned a rule number. As the study is ongoing, additional significant protocol deviations can also be spontaneously identified or defined by the

sponsor and/or the project team during the regularly planned study deviation review meetings and the significant protocol deviations rules document can be updated.

All protocol deviations will be reviewed and assessed as to significance prior to the database lock. The list of protocol deviations (significant or minor) that are additionally considered major clinically relevant for the purposes of analysis will also be identified prior to the database lock.

All major protocol deviations will be summarized using the ITT and mITT sets.

Major protocol deviations will also be presented in a listing.

6. Demographics and Baseline Characteristics

6.1. Demographics

A summary of the following demographics will be presented for the subjects in ITT set and mITT set, respectively.

- Age (years);
- Age group (<18 years, 18 -<36 years, 36 -<50 years, 50 -<65 years, >=65 years);
- Sex (Female);
- Race (White, Black or African American, Asian, American Indian or Alaska Native, Native Hawaiian or Other Pacific Islander, and Other);
- Ethnicity (Hispanic or Latino, Not Hispanic or Latino);
- BMI (kg/m²);
- BMI group (Underweight <18.5 kg/m², Normal 18.5-<25 kg/m², Overweight 25-<30 kg/m², Obese 30-<40 kg/m² and Morbidly Obese ≥ 40 kg/m²).
- BMI group (≤35 kg/m² and >35 kg/m²).

The age collected in CRF will be used for analysis if it is non-missing. If the age is not collected in the CRF, the age in years is calculated using the date of the informed consent and date of birth.

$$\text{Age (years)} = [(\text{Informed Consent Date} - \text{Date of Birth} + 1) / 365.25].$$

BMI is calculated as

$$\text{BMI} = (\text{body weight in kilograms}) / (\text{height in meters})^2.$$

Demographics for all subjects in the ITT set will be presented in a listing.

6.2. Baseline Characteristics

A summary of the following baseline characteristics will be presented for subjects in the ITT and mITT sets, respectively.

- Diabetes mellitus (Yes or No);
- Candida species at baseline (by Genus species);
- Fertility Status (Surgically Sterile/Infertile; Post-Menopausal; Potentially Able to Bear Children);
- Method of Birth Control (Barrier Methods Only; Oral Contraceptives; Depo Contraceptives (Implants/Injectables); IUD; Abstinence; Vaginal Ring; Vasectomized Partner; None; Other);

A separate summary table will be presented to include CLSI MIC range, mode, MIC50, and MIC90, based on the ITT and mITT sets by treatment group for the following MIC results:

- MIC results for SCY-078 and fluconazole (FLU) at 24 hours against candida species isolates obtained at Baseline;
- MIC results for SCY-078 at 48 hours against candida species isolates obtained at Baseline.

Baseline characteristics for all subjects in ITT set will be presented in a listing.

